1.5. Sample Size Justification

Due to the observational nature of the study and recruitment context, it was not possible to predetermine the sample size based on statistical power for estimating the primary and secondary outcomes. Instead, all participants who met the inclusion criteria between September 2019 and February 2022 were included. The final sample has 12,344 deliveries, divided between the MHP and usual care cohorts (with 7147 in one and 5197 in the other, with their identities currently blinded). This represents about 12,287 different participants (we only have information about the percent of multiple deliveries for participants who downloaded the app, 0.464%). Given the sample sizes in the two cohorts, there is 80% power to detect an effect size of 0.051 days. Assuming that the outcomes are normally distributed with a standard deviation of 10 days (1), the study has 80% power to detect a 0.51 day difference in gestational age at birth between the cohorts.

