1.6. Overview of proposed analyses

EG will analyze the primary, secondary, and exploratory outcomes for the trial data. LH will generate data and run models as needed so that EG remains blinded to the identity of each cohort (see section 2.5).

The primary analyses will be multiple linear regression models estimating average treatment effects of the MHP app. Secondarily, dose-response models will be created for the primary and secondary outcomes in order to understand the moderating effects of app usage.

The primary and secondary outcomes for the study will come from electronic health record (EHR) data for trial participants. Given the source and the nature of care for women who deliver in the UPMC system, few outcome data are missing data. As such, imputation will not be used to account for missing outcome data. Instead, participants will be excluded from analyses, if their outcome data is missing for an outcome measure.

As a sensitivity analysis, propensity score matching will be used to create similar cohorts of participants, excluding participants whose propensity scores are outside the overlap in the covariate distributions for the covariates that predict downloading the MHP app (see section 3.1.5). We will calculate average treatment effects for these matched subsets of participants. Inverse probability of treatment weighting will be used as an additional sensitivity analysis to account for the potential lack of overlap in covariate distributions between the study cohorts.

2. Data analysis plan – data description

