3.1. Main analyses of treatment differences

The main analysis compares the mean gestational weeks at birth between the MHP and usual care cohorts. An estimate of the average treatment effect, 95% confidence interval, and effect size will be reported. EG will remain blind to the 80% of outcome data not used to set the terms of the analysis (Section 2.5).

The primary and secondary outcomes will be evaluated at the 5% significance level. No correction for chance will be used for the primary outcome, as there is only one test. For the 9 secondary outcomes, we will report both corrected and uncorrected p-values, using the Bonferroni correction to reduce risk of reporting a false positive result. As a sensitivity analysis, the Bonferroni corrected p-values for ten outcome values will be reported in the supplemental material of the report.

All tests will include all participants with data on the outcome measure involved.

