3.1.1. Analysis of primary outcomes

The difference in gestational weeks at birth will be evaluated using a linear effects model accounting for confounders of preterm birth, as measured at baseline. We estimate that about 57 out of 12,344 deliveries are for a second pregnancy for participants included in the sample given that 0.464% of participants who downloaded the app had two deliveries in the sample. We have included these women in the sample because we cannot exclude similar women in the usual care cohort given limitations in our data. Likewise, we cannot account for random effects of multiple deliveries using a mixed effects model.

Baseline study variables will be included as confounders in the model if (a) the literature has identified the variable as a confounder of preterm birth risk and (b) they might plausibly have influenced participants' decision to download the app. If, for a variable, the evidence on condition (a) is inconclusive and condition (b) is possible, we will examine the data and include the variable if it passes a 10% change-in-estimates threshold for the outcome or for the likelihood of downloading the app. The change-in-estimate will be calculated by adding each study variable to the model from the literature individually. Only baseline variables will be evaluated as potential confounders, as they could not have been affected by use of the app.

We will report the results of two models for each outcome, one using only confounders identified in the literature and one adding confounders identified empirically (Appendix A). Including fewer confounders will reduce the likelihood that the average treatment effect applies only to an unrepresentative subset of the population. Including additional confounders will reduce the likelihood of statistical bias in estimating the average treatment effect.

The dataset contains many known confounders of preterm birth that could be included in the model including:

- Previous preterm birth (3)
- Race (3)
- Low body-mass index (3,4)
- Insurance type (5)
- Area deprivation index (6)
- Multiple gestations (3)
- Previous spontaneous abortions (7)
- Hypertension (3)
- Diabetes (3)
- Tobacco use (3)

There are also many known predictors of preterm birth that are not in the EHRs, hence not available for this study. They include educational attainment, marital status, interpregnancy interval, relatives who delivered preterm, and genetic predictors of preterm birth (3).

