Some collected covariates are specific to this dataset. One is hospital location, which may capture differences in resources, practices, and patient populations. The second is the date of the first visit recorded in Epic, which may capture factors like access to care or social conditions (e.g., the pandemic). We will include hospital location as a variable in all models. We will not include date of first visit as it might be correlated with ones that affect the effectiveness of the app over time.

Residual plots will be used to evaluate the models for heteroskedasticity and the need for using robust standard errors, in order to allow for violations in the assumption that observations are independent and identically distributed (8).

Differences between the cohorts will be described using adjusted mean differences and p-values. Results will be considered significant at $p < 0.05$.

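### The regression coefficient labelled as the average treatment effect need not be that average if the app's effect varies, and fitting fewer confounders is an unreliable way to make it representative.

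*SAP*

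**What the plan says.** SAP section 1.6 states: "The primary analyses will be multiple linear regression models estimating average treatment effects of the MHP app". Section 3.1 makes this the headline result: "An estimate of the average treatment effect, 95% confidence interval, and effect size will be reported". Section 3.1.1 describes a linear model with baseline confounders, reported as one adjusted mean difference. It specifies no cohort-by-covariate terms and no standardisation to a population.

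Section 3.1.1 then announces two models for each outcome. One holds the confounders taken from the literature; the other adds those selected empirically. Neither is named primary. The smaller model is justified thus: "Including fewer confounders will reduce the likelihood that the average treatment effect applies only to an unrepresentative subset of the population". The sentence after it justifies the larger model by reduced bias. Section 3.1 says of the data entering each analysis: "All tests will include all participants with data on the outcome measure involved".

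On whether the effect might vary, section 3.1.1 leaves out the date of first visit because "it might be correlated with ones that affect the effectiveness of the app over time". Inverse probability of treatment weighting is a sensitivity analysis in section 1.6 and is simply to be used in section 3.1.5. Neither section states which population the weights target.

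**The concern.** An average treatment effect is the mean effect over a defined population, here presumably all deliveries in the sample. A main-effects coefficient estimates it if the effect is constant, or if its variation is unrelated to the weights that regression gives implicitly to each covariate pattern. Otherwise women whose probability of downloading is near one half count most, and near-certain downloaders or decliners count least.

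The SAP senses this, since it worries that a fully adjusted estimate may describe an unrepresentative subset. Its remedy is to adjust for less. That does not change who is analysed, because every participant with outcome data stays in. It changes only the implicit weights, and it does so by giving up adjustment. At stake are what the headline number means and which of two unranked models a reader should believe if they disagree.

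**Working it through.** **The plan's own figure.** Section 1.5 assumes outcomes "normally distributed with a standard deviation of 10 days", with cohorts of 7,147 and 5,197, and section 3.1 sets a 5% level. Two-sided testing is inferred from the 95% interval.

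- SE = 10 × √(1/7147 + 1/5197) = 0.182 day.
- Detectable difference = 0.182 × (1.960 + 0.842) = 0.511 day.

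This matches the SAP: "the study has 80% power to detect a 0.51 day difference in gestational age at birth between the cohorts". It is the yardstick below.

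**What the coefficient estimates.** Let stratum x hold a share s of women, with download probability p and effect τ.

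- Average treatment effect = Σ s·τ.
- Main-effects coefficient = Σ s·p(1−p)·τ / Σ s·p(1−p). This is exact when the model is saturated in the covariates and approximate otherwise.

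The SAP gives no download probabilities by covariate, no effect pattern and no confounder strengths. All such values below are assumptions.

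**Size of the weighting gap, smooth case.** Assume a true average of 0.50 day, download logistic in a standardised covariate, and c-statistic 0.70.

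- Effect rising by 0.5 day per SD of that covariate, MHP the larger cohort: the p(1−p)-weighted mean of the covariate is −0.10, so the coefficient is 0.50 + 0.5 × (−0.10) = 0.45.
- The same with MHP the smaller cohort: 0.50 + 0.5 × 0.10 = 0.55.
- Only the third most likely to download benefits, MHP the larger cohort: 0.41.

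The gap is 0.05 to 0.09 day, and its direction can depend on which cohort is MHP. Under the last pattern the coefficient is 0.46 at c = 0.60 and about 0.33 at c = 0.80.

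**Size of the weighting gap, two strata.** Assume 20% of women in stratum X = 1, an effect of 2 days there and 0 elsewhere, and 57.9% downloading overall. The average treatment effect is 0.2 × 2 = 0.40 day. In the last column X also shortens gestation by 5 days and is left out of the model.

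| Download probability, X = 1 / X = 0 | Adjusted for X | X omitted, no outcome shift | X omitted, 5-day shift |
|---|---|---|---|
| 0.15 / 0.686 | 0.26 | 0.10 | 1.86 |
| 0.30 / 0.649 | 0.37 | 0.21 | 1.35 |
| 0.90 / 0.499 | 0.17 | 0.62 | −0.70 |

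First row, adjusted: the weights are 0.2 × 0.15 × 0.85 = 0.0255 and 0.8 × 0.686 × 0.314 = 0.172, so the coefficient is 2 × 0.0255/0.198 = 0.26.

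First row, X omitted with the shift: X = 1 makes up 0.2 × 0.15/0.579 = 0.052 of downloaders and 0.2 × 0.85/0.421 = 0.404 of the others. The raw difference is (2 − 5) × 0.052 + 5 × 0.404 = 1.86.

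Over a wider grid (X share 10% to 30%, download probability in X = 1 from 0.15 to 0.90, either cohort as MHP), the adjusted coefficient ran from 39% to 105% of the average treatment effect. The largest gap was 0.60 − 0.27 = 0.33 day. It vanishes when download probability does not differ by X.

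**A case where fewer covariates help.** Assume X = 1 for 30% of women, effect 2 against 0 days, and download probability 0.6 when X = 0. When X = 1, a variable Z that predicts download only splits women equally into probabilities 0.1 and 0.9. The average treatment effect is 0.60.

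- Adjusted for X and Z: 2 × (0.3 × 0.09)/(0.7 × 0.24 + 0.3 × 0.09) = 2 × 0.027/0.195 = 0.28.
- Adjusted for X only: 2 × (0.3 × 0.25)/(0.7 × 0.24 + 0.3 × 0.25) = 2 × 0.075/0.243 = 0.62.

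Dropping Z costs no confounding here and nearly recovers the average.

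**Does standardisation work?** In 400 simulated samples of 12,344 for each of the first two table rows, an interacted model averaged over the whole sample gave 0.40 and 0.39, as did weighting to the whole sample. The true value is 0.40 and the Monte Carlo error about 0.01. The SD of the estimate was 0.206 against 0.202 for main effects in the first row, and 0.194 for both in the second.

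**The case against.** Linear adjustment is standard, and the weighting gap is small where it can be illustrated: 0.09 day is about half of the 0.182-day standard error. Even the 0.33-day extreme is below 0.51 day. This stands, and it limits the weight of the point.

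A reader might infer that the smaller model only lets confounding back in. The SAP does not support that. The smaller model keeps the literature confounders and hospital, and drops variables for which the literature was inconclusive. The selection rule in section 3.1.1 accepts a variable on a change in either the outcome or the likelihood of downloading, so it can admit pure download predictors, whose removal costs no confounding. The SAP also states the bias trade-off and reports both models.

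A reader might also put a percentage on the smaller model's error. Any such figure simply returns the strength assumed for the omitted confounder, including the 5-day shift above.

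Nor does the SAP say that it expects the effect to vary across women. It raises only possible variation over time, for a variable left out of the primary model. Finally, the matched analysis needs no relabelling, because sections 1.6 and 3.1.5 already describe its result as applying to the matched subset.

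What remains is that the label is not justified by the model specified, and that the reason given for the smaller model is not reliable.

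**Conclusion.** The point holds as a correction to the estimand and to the stated rationale; it is not evidence that the primary analysis is badly biased. The coefficient equals the average treatment effect only if the effect is constant or its variation is unrelated to the implicit weights. Under the assumed patterns, the departure is about 0.05 to 0.09 day at a c-statistic of 0.70 and at most about 0.33 day over the wider grid.

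Reducing the confounder set may bring the estimate nearer to the average or take it further away, depending on whether the dropped variable predicts only download or also the outcome. The SAP does not provide for telling these apart, and the bias from dropping a true confounder cannot be sized from it. A direct method gives the representativeness that the SAP wants without giving up adjustment.

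**What to change.** In section 3.1.1:

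1. Delete the sentence that justifies fewer confounders by representativeness.
2. Name one adjustment set, chosen for control of confounding, as primary; the other model can remain as a secondary report.
3. Define the average treatment effect as the mean over all deliveries in the analysis. Estimate it by adding cohort-by-confounder interactions to the primary model, predicting every delivery under both cohorts and averaging the difference, with a robust or bootstrap confidence interval. List beforehand which terms are interacted, leaving out sparse levels, so that no choice is left until results are seen.
4. Alternatively, state in sections 1.6 and 3.1.5 that the planned inverse probability weighting uses whole-sample average-treatment-effect weights, and take the average treatment effect from that analysis.
5. Describe the main-effects coefficient as an adjusted mean difference under a constant effect.

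The cost is SAP wording and a few lines of R, a slightly larger standard error (about 1% at c = 0.70, about 2% in the more extreme simulated case, 0.206/0.202), and more model terms. Standardisation does not replace a confounder that was left out, so step 2 is needed as well as step 3.

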3.1.2. Analysis of secondary outcomes

Analytical procedures for the secondary outcomes will follow those for the primary outcome. Each outcome will have its own appropriate confounders. As with the primary outcome, these confounders will be based on previous research and specified a priori. As needed, they will be supplemented by empirical analysis of the 20% subset, including baseline covariates specified in Appendix B, with a 10% change-in-estimate threshold for inclusion.

These confounders from the literature are available:

1. Preterm birth defined as delivery before 37 gestational weeks.
 - a. Same confounders as the primary outcome
2. Clinical diagnoses of depression.
 - a. History of anxiety and depression (9)
 - b. Smoking (9)
 - c. Past pregnancy complications or loss (9)

Unavailable: Lack of partner or social support or having a problematic relationship, a history of abuse or child abuse, having had an unplanned or unwanted pregnancy, perceived stress, cognitive style (including “pessimism, anger and rumination; a tendency to be nervous, worried or shy; low self-esteem and low self-efficacy; and high levels of neuroticism or psychoticism”), and single marital status (9).
3. Anxiety rates (using ICD10 codes).
 - a. History of anxiety and depression (9)
 - b. Smoking (9)
 - c. Past pregnancy complications or loss (9)

Unavailable: Same as anxiety (9).
4. Referral to behavioral health
 - a. No confounders identified
5. Referral to social work
 - a. No confounders identified
6. Preeclampsia
 - a. Prior pre-eclampsia (10)
 - b. Chronic hypertension (10)
 - c. Pre-gestational diabetes (10)
 - d. BMI >30 (10)

Unavailable: Antiphospholipid antibody syndrome (10).
7. Sufficient gestational weight gain
 - a. Pre-pregnancy BMI (11)
 - b. Age (11)

Unavailable: Family violence; marital status; food insecurity; maternal pregravid metabolic status; hyperemesis gravidarum; anorexia; past bariatric surgery (11).
8. Number of prenatal appointments attended
 - a. No confounders identified
9. Percent of required prenatal appointments attended
 - a. No confounders identified

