Appendix A

Covariates and Outcomes

Variable Name in EHR	Description	Variable type
PATIENT_ID	ID for each patient not related to patient information	ID
MOM_AGE	Mother's age at time of delivery	Baseline covariate
FINANCIAL_CLASS	Payor at time of delivery from Medipac (insurance level, might be like coverage) (i.e. name like 'UPMC HEALTH NETWORK', 'MED PLUS', 'BEST HEALTH CARE', etc)	Baseline covariate
HOSP_ROLLUP_GROUPING1	Payor at time of delivery from Medipac (insurance type) (i.e. specifies type of UPMC insurance, examples include 'UPMC Commercial', 'Other MA Managed', 'Other Commercial', etc)	Baseline covariate
HOSP_ROLLUP_GROUPING2	Medicare, Medicaid, Self-pay, or Commercial Insurance	Baseline covariate
HPFLAG	Payor at time of delivery from Medipac (UPMC Health Plan Member flag, 1= has UPMC Health Plan, 0=Doesn't have it)	Baseline covariate
PT_ZIP	Patient zipcode	Baseline covariate
AD_ZIP_4	Patient zipcode, location extension (+4)	Baseline covariate
ADI_NATRANK	Area deprivation index, national ranking (0 most deprived, 100 least deprived)	Baseline covariate
RACE	Race, as reported through UPMC	Baseline covariate
MOM_HEIGHT	mother's height at time of delivery (cm)	Baseline covariate
OB_GRAVIDITY	Number of pregnancies (includes current pregnancy, so if it's their first pregnancy, this will be a 1)	Baseline covariate
OB_PARITY	Number of previous deliveries (will be 0 if it's their first pregnancy)	Baseline covariate
OB_FULL_TERM	Number of previous full term pregnancies	Baseline covariate
OB_PREMATURE	Number of previous premature deliveries (prior to 37 gestational weeks)	Baseline covariate
OB_ABORTIONS	Number of previous abortions, including therapeutic/spontaneous abortions	Baseline covariate
OB_LIVING	Number of previous live deliveries	Baseline covariate
OB_SPONTANEOUS_AB	Number of previous miscarriage/spontaneous abortions	Baseline covariate
OB_THERAPEUTIC_AB	Number of previous therapeutic abortions	Baseline covariate
PREGRAVID_WEIGHT	mother's pre-pregnancy weight (kg)	Baseline covariate
GESTAGE_ATVISIT_DAYS	This is the gestational age of the pregnancy at the time of prenatal visit. Calculated using the estimated delivery date ((280-(EPISODE.OB_WRK_EDD_DT-pat_enc.contact_date))).	Baseline covariate
PREGSTART_OBESE	Obese BMI at first prenatal visit (binary variable)	Baseline covariate
PREGSTART_MORBIDOBSE	Morbidly obese BMI at first visit (binary variable)	Baseline covariate

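### BMI is listed as a one-sided threshold for gestational age, preterm birth and preeclampsia although weight and height are recorded; coded that way, the literature-only model under-adjusts for it

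*SAP*

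**What the plan says.** For the primary outcome, SAP section 3.1.1 introduces its list with "The dataset contains many known confounders of preterm birth that could be included in the model including", and the BMI entry is "Low body-mass index (3,4". No cut-off for low and no functional form is given. Section 3.1.2 item 1 carries this list over to preterm birth. Item 6 (preeclampsia) lists BMI above 30. Item 7 (gestational weight gain) lists "Pre-pregnancy BMI (11" with no threshold.

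Appendix A records PREGRAVID_WEIGHT, described as "mother's pre-pregnancy weight (kg", and MOM_HEIGHT in cm. It also has binary flags for obesity and morbid obesity at the first prenatal visit, but no low-BMI flag and no BMI variable.

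Section 3.1.1 commits to two models per outcome. One holds only confounders from the literature. The other adds variables that pass a 10% change-in-estimate rule, assessed on the unblinded 20% subset. Section 3.1.5 adds propensity matching and inverse probability weighting, again without a form for BMI.

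**The concern.** The cohorts are self-selected: one downloaded the app, the other did not. They may well differ in BMI, and the SAP itself treats BMI as a confounder. A low-BMI indicator puts normal-weight, overweight and obese women into one reference group. An indicator above 30 treats all women below 30 alike, and all women above it alike. Any BMI difference between the cohorts within those groups stays in the adjusted cohort difference.

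The low-BMI term has to be derived from weight and height, so the continuous measure is already at hand, and item 7 shows that the plan is willing to use BMI uncut. At stake are the primary outcome and two secondary outcomes, preterm birth and preeclampsia. Weight gain is not affected.

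**Working it through.** **1. The plan's own precision.** Inputs from section 1.5: cohorts "with 7147 in one and 5197 in the other", and "Assuming that the outcomes are normally distributed with a standard deviation of 10 days (1". Section 3.1 gives the level: "The primary and secondary outcomes will be evaluated at the 5% significance level". It does not state sidedness; two-sided is assumed.

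- SE = 10 × √(1/7147 + 1/5197) = 10 × 0.01823 = 0.182 days
- Detectable difference = (1.960 + 0.842) × 0.182 = 0.51 days

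This reproduces the statement that "the study has 80% power to detect a 0.51 day difference in gestational age at birth between the cohorts".

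**2. What a cut keeps, by formula.** For a normal covariate split at quantile z with a fraction p beyond the cut, the share of linear information kept is φ(z)² / [p(1 − p)].

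- p = 0.03: 0.0680² / 0.0291 = 0.16
- p = 0.05: 0.1031² / 0.0475 = 0.22
- p = 0.30: 0.3477² / 0.21 = 0.58

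A cut at the lowest 3-5% therefore leaves about 78-84% of linear BMI confounding. A cut with 30% above it leaves about 42%.

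**3. The same question with skewed BMI and other shapes.** The SAP gives no BMI data, so every input here is an assumption: log-normal BMI with mean/SD 26/5.5, 27/6.5 or 28.5/7.5; a cohort gap of 0.1, 0.2 or 0.3 SD; low BMI taken as below 18.5 and morbid obesity as above 40. The outcome depended on BMI alone and was regressed on cohort by least squares, with 1.5 million records per scenario. Share of the crude BMI bias left:

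| BMI term in the model | Linear | High-side only | J-shaped | Low-side only |
|---|---|---|---|---|
| Low-BMI indicator | 77-80% | 88-90% | 95-100% | 33-41% |
| Indicator above 30 | 36-46% | 28-31% | 22-38% | 65-77% |
| One linear BMI term | 0% | −4 to −6% | −11 to −16% | 11-19% |

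Low, above-30 and above-40 indicators together leave 13-31% across all shapes. A negative share means over-correction. A single linear term is therefore much better than a cut but not sufficient when the relation is curved.

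**4. Can the extended model be relied on to repair this?** The 20% subset is 0.20 × 12,344 ≈ 2,469 deliveries, about 1,234 per cohort when split evenly. There the SE of the cohort difference is 10 × √(2/1234) = 0.40 days, so a percentage change in that estimate is unstable.

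The rule was simulated with the low-BMI flag already in the model, assumed slopes of 0.1-0.3 days per BMI unit and gaps of 0.1-0.2 SD. The question was whether the obesity flag or pre-pregnancy weight passes.

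- No app effect: one of them passes in about 62-67% of runs at the smallest slope and gap, and in nearly all runs at the largest.
- True 0.51-day effect: about 36-51% at the smallest, and about 99% at the largest.

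The ranges at the smallest corner reflect different assumed BMI inputs. Entry is likely where the bias is large, but it is not assured.

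**5. Size in days, as illustration only.** With an assumed linear slope of 0.05-0.2 days per BMI unit, a gap of 0.1-0.3 SD and SD 6.5, the crude bias runs from 0.05 × 0.1 × 6.5 = 0.03 to 0.2 × 0.3 × 6.5 = 0.39 days. With about 77-78% left (linear row, SD 6.5), 0.03 to 0.30 days remain. The slope and gap come from outside the SAP, so this is not a finding about the trial.

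**The case against.** The best reply is that the SAP never says BMI enters as a threshold. The primary list is permissive and names risk factors as the literature describes them; coding is left open. That stands. A reader might infer a fixed model with a fixed reference group, and the text does not go that far. But section 3.1.1 also says that variables meeting its two criteria will be included, and section 3.1.2 describes the confounders as specified a priori. Either the terms are coded as listed and under-adjust, or the form of a named confounder is unfixed. The same edit cures both.

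Second, the extended model can bring in obesity flags, weight or height, and the matching and weighting analyses are further checks. This also stands, so a reader should not conclude that the confounding remains in every reported comparison. It does not protect the literature-only model, which is reported in its own right. Even three BMI indicators together leave 13-31%, and the propensity model states no form for BMI either.

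Third, hypertension and diabetes are on the primary list, and chronic hypertension, pre-gestational diabetes and prior preeclampsia on the preeclampsia list. They will absorb part of any effect of high BMI, so the shares above are probably too high. The literature cited for the primary outcome concerns low BMI, and if BMI acts only there the share left is 33-41%.

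Finally, one might read the illustration in days as bias amounting to more than half of the detectable 0.51 days. The documents do not support that: they give no BMI gap, slope or shape.

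**Conclusion.** The point holds for the literature-only model, if its BMI terms are coded as listed. That model leaves most of the BMI confounding for gestational age and preterm birth under linear, high-side or J-shaped relations, and roughly a quarter to a half for preeclampsia. If BMI acts only at its low end, the order reverses: about a third to two fifths remains for the first two outcomes and two thirds to three quarters for preeclampsia.

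The shares vary little over the assumed distributions and gaps but depend on the assumed shape, and they take no account of correlated covariates. The absolute bias cannot be derived from the SAP. This is a worthwhile, inexpensive improvement to the adjustment, not evidence that the primary result will be wrong.

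**What to change.** In section 3.1.1, in section 3.1.2 item 6 (and item 1 by reference) and in the propensity model of section 3.1.5, replace the threshold terms with continuous pre-pregnancy BMI computed from PREGRAVID_WEIGHT and MOM_HEIGHT. Enter it as a restricted cubic spline, or as linear plus quadratic, in both reported models. The threshold categories can stay in the baseline table.

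State how the missing pre-pregnancy weights (1318/13752 = 9.6%) are handled under section 2.4, including whether weight is imputed before BMI is computed. That section allows median or multiple imputation, depending on the apparent mechanism. Median-imputed weight would itself leave some BMI confounding among the women concerned.

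The cost is revised wording, one derived variable and two or three model terms, with no new data. The downside is that BMI inherits the missing weights; a low-BMI term derived from the same weights would inherit them too.
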